### **Randomization and blinding**

Participants are randomly assigned to either the treatment (SIESTA+TAU) or control (TAU) group with a 1:1 allocation stratified by ADHD medication use (yes/no) and location (Leuven, Antwerp, Hasselt, Brussels, Gent, Roeselare) using permuted blocks of random sizes.[34,35] We randomize per location to ensure practical feasibility for our therapists of the KU Leuven (i.e. there is a maximum amount of adolescents that can be treated per location). Randomization is done by an

independent researcher who is not involved in the study in any way. Due to the nature of the psychological treatment neither participants nor clinicians can be blinded to allocation. Researchers who are responsible for the practical side of the study (LK, FM), are not blinded to allocation, however, the principal investigator ([name]) and the other researchers DB, BB and MD are blinded throughout the study.

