### **Sample size estimates**

A recent study in typically developing adolescents with sleep problems found large effects ( $\beta = 0.91$ ) at post-test of a CBT sleep treatment as compared to waitlist controls on their primary sleep related outcome measure (objectively measured) and a medium effect size for reduction of ADHD symptoms[13,14]. Based on this research, moderate to large effect sizes can be expected for SIESTA in combination with TAU for ADHD on sleep outcomes as compared to TAU for ADHD only. Therefore, using G\*power we calculated with this large effect size a power of .8 and an alpha of .5 for our desired sample size. There are at least 40 participants per condition needed for analyzing the data implementing a linear mixed effects model. However, to anticipate for possible drop-out or lack of response on assessment (although expected to be minimal due to inclusion of motivational interviewing and the pilot study) and as the effect size of the ADHD outcome is medium and not large

[d=.55] an additional 15% will be recruited. Resulting in a total of 92 participants, with 46 participants per condition.

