
When the adolescent meets inclusion criteria, the adolescent has to fill out the pretest questionnaires in Qualtrics. Parent(s)/guardian(s) of the adolescent are also asked to answer questionnaires in Qualtrics; also, they are asked to mail the link of the questionnaire (CPS) in Qualtrics to the teachers of the adolescent for their evaluation of the adolescent. Moreover the teacher will be asked how many lesson times per week he/she has contact with the participant. The names of the teachers will not be known by the researchers.

After the pretest is conducted, appointments for the treatment are made. However, participants are informed that those appointments can either happen as planned or that the treatment will take place 6 months later, due to the condition their child was assigned to. To avoid the possibility of a systematic bias in the assignment of participants to both groups (SIESTA treatment and treatment as usual (TAU) versus TAU only), randomization happens. We will use a stratified permuted block randomization based on medication use (yes/no) in blocks of 2 participants whereby an independent researcher performs the randomization. After the last treatment session, both the adolescent who followed the treatment and the paired adolescent from the TAU-group, are contacted by the researchers and provided with the actigraphs. The daily sleep logs are again filled out in Qualtrics. Within one week after the last treatment session a posttest session is planned in which the adolescent and parent(s)/guardian(s) are asked to fill out the questionnaires in Qualtrics. Filling out the questionnaires should not take longer than 1 hour for any informant. The actigraphs will again be picked up by a researcher or the courier service. The same procedure is applied during the follow-up measure after 3 months, including the actigraph/daily logs and the questionnaires. After follow-up, the treatment is provided to the adolescent in the TAU-group from that block.

In case of serious adverse events or a crisis situation, e.g. suicidality, during any phase of the study, (previously involved) clinicians will be contacted by the researchers. Also, if necessary at any time of the study, additional psychological aid can be given.

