### **Statistical analysis**

The analyses are based on an intent-to-treat approach, whereby participants are analyzed as a function of the condition to which they had been assigned. A longitudinal linear mixed effects model will be applied, with the variance components error correlation structure among the repeated measures over pre-test, post-test, and follow-up. The model contains a random intercept varying over participants, a fixed effect of time (pre-test, post-test and follow-up), a random slope for time varying over participants, a fixed effect of condition (1 = SIESTA+TAU; 0 = TAU), and an interaction effect between time and condition. We will correct for multiple testing in the multilevel analyses. Additionally, the potential impact of COVID-19 restrictions is taken into account by including wave as a level in the multilevel analyses. Effect sizes (ESs) are computed by calculating the difference in change scores for SIESTA+TAU as compared to TAU only between post-treatment/follow-up and pre-test and dividing this amount by the pooled standard deviation of the change scores for SIESTA+TAU and TAU only. Confidence intervals for ESs are computed using procedures delineated by Odgaard and Fowler (2010).[56] Although participants are instructed to be off sleep medication and to not change their ADHD medication, they may not comply. Therefore, this is thoroughly assessed both at

post-test and follow-up. This allows for potential sensitivity analyses in the sleep medication free sample, and those that did not change ADHD medication.

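### The mixed model leaves the arms' pre-test means free, so the treatment contrast is a change-score difference: unbiased, but less precise than a model with a common pre-test mean

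*Combined protocol and SAP*

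**What the plan says.** The Statistical analysis section specifies a longitudinal linear mixed model with a "variance components error correlation structure among the repeated measures over pre-test, post-test, and follow-up". Pre-test is thus part of the outcome vector. The model has a random intercept, "a random slope for time varying over participants", a fixed effect of time, and "a fixed effect of condition (1 = SIESTA+TAU; 0 = TAU), and an interaction effect between time and condition". The section does not say whether time is categorical or linear.

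The effect size is obtained by "calculating the difference in change scores for SIESTA+TAU as compared to TAU only between post-treatment/follow-up and pre-test", divided by the pooled SD of the change scores. Nowhere do the documents adjust for the pre-test value or set the pre-test means equal.

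Two design features bear on this. The Randomization and blinding section describes "1:1 allocation stratified by ADHD medication use (yes/no) and location". The Ethics & procedure section says "After the pretest is conducted, appointments for the treatment are made", then explains that the timing of treatment depends on the assigned condition, and only then describes the randomisation.

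**The concern.** A condition main effect alongside a time-by-condition interaction gives each arm its own pre-test mean. The interaction then measures how far each arm moved from its own starting point. If allocation is random and follows pre-test, any pre-test difference between arms is chance. A change score subtracts all of that chance difference, although only the part that predicts the later value needs removing.

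What is at stake is precision. The Sample size estimates section plans on 40 participants per condition before inflation and acknowledges that the ADHD-symptom effect is only medium. The Statistical analysis section also promises a multiplicity correction. Pre-test values are collected anyway, so precision lost this way can be recovered without new data.

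**Working it through.** **Inputs from the documents.** 1:1 allocation; three occasions; 40 per condition before inflation (40 x 1.15 = 46 after it); planning effects of 0.91 for sleep and 0.55 for ADHD symptoms.

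**Assumed, because the documents do not say.** The pre-post correlation rho; the ratio k of post-test to pre-test SD; both effects in baseline-SD units; two-sided alpha of .05 (the text prints .5) with no multiplicity correction.

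**The plan's own figure.** An effect of 0.91 at 80% power and two-sided .05 needs 20 per condition by an exact two-sample t calculation, so the stated 40 does not follow from it. That is a separate matter; 40 is used here only as the stated group size.

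**Step 1: is the planned contrast a change score?** Generalised least squares on three occasions, with categorical time and free pre-test means, was run under six random-intercept and random-slope covariance settings. With complete data, the interaction at each later visit had exactly the variance of the difference in mean change in all six. Constraining the pre-test means to be equal lowered the variance in all six, with ratios from 0.65 to 0.94.

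**Step 2: variance per participant, with pre-test SD = 1 and post-test SD = k.**

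- Change score: 1 + k² − 2·rho·k
- Adjusted (common pre-test mean, large sample): k²(1 − rho²)
- Difference: (1 − rho·k)², which is never negative and is zero when the slope of post-test on pre-test, rho·k, equals 1

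At k = 1 the ratio of adjusted to change simplifies to (1 + rho)/2.

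| rho | k = 1 | k = 1.2 |
|---|---|---|
| .3 | 0.91/1.40 = 0.65 | 1.310/1.72 = 0.76 |
| .5 | 0.75/1.00 = 0.75 | 1.080/1.24 = 0.87 |
| .7 | 0.51/0.60 = 0.85 | 0.734/0.76 = 0.97 |

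The loss is largest at low correlation. Using pre-test as a covariate spends one parameter, a factor of about 1 + 1/(80 − 4) = 1.013 at 40 per arm, which moves the k = 1 ratios to 0.66, 0.76 and 0.86. A simulation of 20,000 trials at 40 per arm gave 0.65, 0.76 and 0.86, with both estimators centred on the true 0.55.

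**Step 3: power at 40 per arm, k = 1, noncentral t.** The standardised effect is the difference divided by the square root of the Step 2 variance. At rho = .5 and a difference of 0.55, it is 0.55/√1.00 = 0.55 for the change score and 0.55/√0.75 = 0.635 adjusted.

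| rho | 0.55: change → adjusted | 0.91: change → adjusted |
|---|---|---|
| .3 | 54% → 72% | 92.5% → 98.8% |
| .5 | 68% → 80% | 98.0% → 99.6% |
| .7 | 88% → 93% | 99.9% → about 100% |

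**The case against.** The strongest reply is that nothing planned is invalid. Under randomisation the interaction is unbiased, and a change-score effect size is coherent with the model. This stands. A reader might infer that chance pre-test imbalance biases the planned estimate. It does not: over repeated randomisations the error averages to zero, and what is lost is precision.

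Second, the larger power gains belong to a secondary outcome. At the effect planned for sleep, power under the planned contrast is already above 92% in every case shown. This stands too.

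Third, the size of the gain rests on unstated quantities. The planned random slope allows variance to grow after pre-test, and with k = 1.2 much of the gain disappears. If 0.55 is instead in units of the SD of change, which is how the Statistical analysis section standardises, planned power at 40 per arm is 68% whatever rho is. A reader might infer that adjustment secures 80% power. The documents do not support that: the 80% needs rho = .5, equal SDs and the baseline-SD scale, and it ignores the planned multiplicity correction.

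Fourth, one might argue that selecting on poor sleep implies moderate correlations, where change scores lose most. Neither part holds. The loss is greatest at low correlation, and the sleep criteria do not select on outcomes such as homework problems or classroom performance.

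Finally, the procedure text implies that pre-test comes before randomisation but does not say that teacher forms, forwarded by parents, are returned before allocation is known. That limits the constraint for the teacher-rated scale.

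**Conclusion.** The point holds as lost efficiency, not as an error. The plan estimates a pre-test difference that the design makes zero in expectation. Under equal SDs this leaves 15% to 35% of the contrast's variance removable for rho between .7 and .3; at a post-test SD 1.2 times the pre-test SD, it is 3% to 24%. The loss vanishes when the post-on-pre slope is 1, so it need not be material for every outcome. In power terms it could matter for an effect of 0.55 baseline SD and matters little at 0.91.

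The conclusion that precision can be gained without bias rests on randomisation and on pre-test being completed before allocation is known. The size rests on rho and the SD ratio, which the documents do not give. The exact equality with a change score also needs complete data and categorical time; under linear time the contrast would be a difference in slopes, still with free pre-test means. This is a free improvement using data already collected.

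**What to change.** State that time is categorical. Omit the condition effect at pre-test, keep condition-by-post-test and condition-by-follow-up terms, and report those two contrasts with their confidence intervals as the main effects. Keep the change-score effect size as a descriptive figure, so that the headline estimate and the model agree.

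Prefer this baseline-constrained mixed model to entering pre-test as a covariate. The two are not interchangeable when pre-test values are missing: the covariate form drops those participants, while the constrained form keeps them, which suits the intention-to-treat aim.

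For the teacher-rated scale, apply the constraint only if the pre-test form was returned before allocation was known, and record the return date so that this can be checked.

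The cost is a few sentences in the analysis section, a changed model statement, and a revised description of the reported effect. No new data are needed. It should be settled before any analysis by arm.

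### The listed model leaves out the factors that randomisation is stratified by, and the wave term does not say whether wave may act on change; the likely cost is lost power, not bias

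*Combined protocol and SAP*

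**What the plan says.** The documents describe the randomisation twice. Under Randomization and blinding, participants are allocated "with a 1:1 allocation stratified by ADHD medication use (yes/no) and location", with six locations named and permuted blocks of random sizes. The reason given for using location is practical: "We randomize per location to ensure practical feasibility for our therapists". Under Ethics & procedure, the scheme is a "stratified permuted block randomization based on medication use (yes/no) in blocks of 2 participants", and location is not mentioned.

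The Statistical analysis section specifies a longitudinal mixed model with a participant random intercept, fixed time, a participant random slope for time, "a fixed effect of condition (1 = SIESTA+TAU; 0 = TAU), and an interaction effect between time and condition". Neither baseline medication use nor location is listed. Medication returns only in possible sensitivity analyses of participants free of sleep medication or with unchanged ADHD medication. Those subsets are not the baseline stratum.

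On the pandemic, the section states that "the potential impact of COVID-19 restrictions is taken into account" by "including wave as a level in the multilevel analyses". It does not say whether that level carries an intercept, a slope for time, or both. Study design lists five recruitment waves between January 2021 and March 2023. Effect sizes are defined on change scores, with no adjustment stated.

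**The concern.** Stratified randomisation balances the arms on the stratification factors. If those factors predict the quantity being compared, the treatment estimate varies less from one randomisation to the next than an analysis ignoring them assumes. The unadjusted model leaves that variance in its standard error, so intervals are too wide and power is lost. Both factors could plausibly matter. The Intervention and comparison section says that usual care is mainly stimulant medication, and location is where the therapy is delivered.

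The wave term raises a related question. The treatment effect is read from time by condition, which is a contrast of change. Restrictions that differ between pre-test and later visits act on change. A term that moves all three visits of a wave by the same amount cannot represent that. If this is what is meant, the section claims an adjustment that the model does not make.

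**Working it through.** **Inputs.** The strata are medication (2 levels) and location (6 levels), from Randomization and blinding, or medication only, from Ethics & procedure. There are five waves (Study design). Sample size estimates gives 40 per condition before inflation and 40 × 1.15 = 46 after it, so 92 in total. The plan prints no figure for how much variance the strata or wave explain, so there is none to reproduce. The shares below are assumptions.

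**Step 1: which variance matters.** Write a participant's outcome at visit t as a stable part (participant, wave, medication and location levels) plus a part that depends on t. In post-test minus pre-test, every stable term is subtracted from itself and vanishes. This holds for a wave intercept and equally for stable differences between medication groups or locations. Only the part of strata or wave that predicts change can affect the time by condition result.

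A generalised least squares check (92 participants, 3 visits, complete data, fixed variance components, one illustrative data set) gave these time by condition estimates and standard errors at post-test / follow-up:

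| Model | Estimate | SE |
|---|---|---|
| Listed terms, no wave | 0.21605 / 0.28277 | 0.21869 / 0.24672 |
| + wave random intercept | 0.21605 / 0.28277 | 0.21869 / 0.24672 |
| + strata main effects | 0.21605 / 0.28277 | 0.21869 / 0.24672 |
| Wave intercept and wave-level random change | 0.47287 / 0.53959 | 0.22914 / 0.25603 |
| Strata × time | 0.21916 / 0.28588 | 0.22461 / 0.25198 |

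The first three rows are identical. Results move only when wave or strata may act on change.

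**Step 2: size of the standard error problem.** Let R² be the share of the variance of change (or of the pre-test-adjusted outcome) that stratification balances. The model SE divided by the true SD of the estimate is 1/√(1 − R²). The actual size of a nominal two-sided 5% test is 2[1 − Φ(1.96/√(1 − R²))].

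- R² = 0.10: 1/√0.90 = 1.054; 1.96 × 1.054 = 2.066; size 0.0388.
- R² = 0.20: 1/√0.80 = 1.118; 1.96 × 1.118 = 2.191; size 0.0284.
- R² = 0: ratio 1, size 0.05.

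**Step 3: if only medication was a stratum.** Suppose the strata effects on change are split equally between medication and location. Only half the share is then balanced: 1/√0.95 = 1.026 and 1/√0.90 = 1.054. A simulation with that split gave inflation of about 2% and 5%.

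**Step 4: simulation of the change-score contrast.** This used N = 92, five waves, both randomisation descriptions and 4,000 replicates per scenario (Monte Carlo SE near 5%: √(0.05 × 0.95/4000) = 0.0034). Strata and wave were each assumed to explain 0–20% of the variance of change.

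- Neither predicts change: model SE / true SD is 0.99–1.01 and type I error 0.046–0.051.
- Strata and wave together explain 10–30%: the ratio is about 1.00–1.13 and type I error 0.029–0.045.
- Power at d = 0.55, the medium effect in Sample size estimates: 0.73–0.77 as listed, and 0.73–0.87 with strata and wave as predictors of change. After that change, type I error is 0.044–0.054. The largest gain is about 10 points (0.772 to 0.868, with strata at 20% and wave at 10%).

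**Step 5: cost in degrees of freedom.** Medication 1, location 5 and wave 4 make 10. With 40 per arm, 80 − 2 (intercept and condition) − 10 = 68. The critical t moves from 1.991 (78 df) to 1.995 (68 df).

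Missing data and small-sample degrees-of-freedom methods were not simulated.

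**The case against.** The strongest reply is that nothing here threatens validity. The participant random intercept already absorbs stable differences between medication groups and locations. With time-invariant strata effects of 10% and 20% of outcome variance, a simulation under medication-by-location stratification gave type I error of 0.050–0.055 and SE ratios of 0.99–1.01. A reader might infer that the plan's standard errors are simply wrong. The documents do not support that: they are too large only if the factors predict change, and no share is given. This part of the reply stands.

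A reader might also infer that the COVID-19 adjustment fails. That assumes a wave intercept only, which the section does not say. The same paragraph gives participants a random slope for time, and a slope at wave level would act on change. This stands too, so the criticism is under-specification. Nor does a wave effect common to both arms bias the treatment contrast. Five waves make a variance component imprecise, but nothing computed here shows that it would be estimated at zero or fail to converge.

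Finally, the gain from adjusting is not assured. The lower end of the power range does not move, and in the illustrative data set the strata × time terms raised the SE. That is a fair statement of the downside. It does not answer the mismatch between how the trial randomises and how it plans to analyse, or the open meaning of the wave term.

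**Conclusion.** The point holds in a limited form. The listed model omits the stratification factors named under Randomization and blinding, and the wave term leaves open whether change is adjusted. If the factors predict change, the time by condition test is conservative: SEs are about 5% or 12% too large, and the test runs at about 3.9% or 2.8%, under assumed shares of 10% or 20% of the variance of change. If they do not, the SEs are correct. The randomised comparison is unbiased either way. With medication as the only stratum, the inflation is smaller.

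Read as a random intercept alone, wave would not take account of restrictions that changed between pre-test and later visits, and its variance would rest on five units. The cancellation is exact with complete data. Confidence is moderate, because the size depends on an unknown share, on which randomisation description is correct, and on an unstated detail of the wave term.

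**What to change.** 1. Reconcile Randomization and blinding with Ethics & procedure, and state once which factors and block sizes were used.
2. Add the actual stratification factors and wave as fixed effects, each interacting with time, or use them as covariates in a pre-test-adjusted model. Main effects alone in the listed model would leave time by condition unchanged with complete data.
3. Replace the wave level with these fixed terms, so that the text shows how wave can act on change.
4. Pre-specify a pooling rule for sparse locations. An even spread would give 92/6 ≈ 15 participants per location and 92/12 ≈ 8 per medication-by-location cell, and actual numbers may be more uneven.

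Medication use, location and wave are already recorded, so the change is analysis wording and a few model terms. The statistical cost is about 10 degrees of freedom and a slightly larger SE if the factors do not predict change. In one such simulated scenario the mean SE rose from 0.2077 to 0.2146 (about 3%) and power at d = 0.55 fell from 0.751 to 0.726.

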### **Ethics and dissemination**

#### **Ethical considerations**

The study application was submitted to the Ethical Committee Research UZ/KU Leuven. The study activities and informed consent forms have been approved. The study will be conducted according to ethical principles based on the Helsinki Declaration, good clinical practice (GCP), national regulatory mandatory instructions and this protocol. GDPR General Data Protection Regulation (or GDPR) ((EU) 2016/679 of 27 April 2016; <https://eur-lex.europa.eu/eli/reg/2016/679/oj>) will be applied as the adolescents and their parents are informed about the study and the informed assent and consent form are presented in understandable language before participation. Adolescents are asked assent to participate in the study (Supplement 2). Additionally, consent from the parent is required for participation (Supplement 3).

